Trial size: 2 x 1675 patients are required to show a 20% relative risk reduction or increase (5% absolute risk reduction or increase) in the primary outcome measure, assuming a baseline 90-day mortality of 25% ($\alpha=0.05$ (two-sided), and $\beta=0.1$)

Time schedule:

2014 – November 2015: Governance approval applications, education of trial sites, other preparations

December 2015: First Danish patient enrolled

February 2015: Commencement of inclusion in other countries

[figure not shown]
November 2017: Last patient enrolled

January 2018: Follow-up completed

May 2018: Data analysis and submission for publication

Trial flow chart

The flowchart (n=) will be filled in during or at the end of the trial.

Administrative information

The research programme organisation is attached in *appendix 1*

Sponsor

[name]

Department of Intensive Care 4131

University hospital of Copenhagen Rigshospitalet

[name]

E-mail: [contact]

[contact]

Trial sites

Clinical sites:

ICUs in:

- Denmark
- Finland
- Iceland
- Italy
- Norway
- Switzerland
- The Netherlands
- United Kingdom

Methodological and statistical site:

Copenhagen Trial Unit (CTU), Rigshospitalet, Copenhagen, Denmark

Department of Biostatistics, Copenhagen University, Denmark

Steering Committee

The Steering Committee consists of the Management Committee and the National Principal Investigators (*appendix 1*)

Management Committee:

Sponsor:

[name] [name] PhD
Department of Intensive Care 4131
Copenhagen University hospital Rigshospitalet
Denmark

Coordinating investigator:

[name]
Department of Intensive Care 4131
Copenhagen University hospital Rigshospitalet
Denmark

[name], professor, MD, PhD
Department of Intensive Care 4131
Copenhagen University Hospital Rigshospitalet
Denmark

[name], PhD
Copenhagen Trial Unit (CTU)
Copenhagen University Hospital Rigshospitalet
Denmark

National principal investigators:

[name], PhD
Department of Anaesthesia and Intensive Care
Landspítali University Hospital, Reykjavik
Iceland

[name], professor, MD

Department of Anaesthesia and Intensive Care, Haukeland University Hospital, Bergen
Clinical Institute 1 UiB, Bergen University Hospital
Norway

[name], PhD
Department of Critical Care
University of Groningen, University Medical Centre of Groningen
The Netherlands

[name]
Department of Intensive Care
University Hospital Bern
Switzerland

[name], PhD
Department of Adult Critical Care

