1.6.2 Sample size considerations

It is difficult to produce reliable sample size estimations according to anticipated effects on GI bleeding because we have no reliable control groups due to the widespread use of PPI [57] and previous trials are in fact very old. As a consequence it has been necessary to calculate sample size estimations given that something may change if we stop/avoid PPI until GI bleeding actually happens (see *appendix 11*). The addressed intervention effect of 20% RRR or RRI on the primary outcome may seem high, but in a population with septic shock or in e.g. patients after cardiac arrest a 20% hazard ratio reduction corresponds to 1 months of extra median survival in patients with a median survival of approximately 5 months. So after all, a 20% RRR or RRI may not be as huge as could be anticipated, when it only results in a modestly longer survival in these patients. The power for even major effects on each of the possible side effects (pneumonia, CDI and acute myocardial ischemia) are small, but it will still be a large contribution to our knowledge on these outcomes that may seriously question, overthrow or confirm what we know so far. Furthermore, 3,350 patients included in one trial would be a huge contribution to the evidence, more than doubling the number of randomised patients and providing trial results with low risk of bias on mortality and serious adverse events.

No single trial, however big or well done, gives the final answer, and the SUP-ICU trial will not be an exception. However, the results will inform clinicians, guideline committee members and policy-makers on the use of PPI in the ICUs, as well as establish more (reliable) trust in PPI. Should we find 10-20% relative risk increase in mortality this will certainly trigger a new wave of trials on PPI or SUP in general and even though our trial may not be conclusive it may eventually lead to conclusions.

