11.1 Sample size estimation and power calculations

11.1.1 Sample size estimation for the primary outcome

Primary outcome measure

Assuming a baseline 90-day mortality of 25% [9] (see *appendix 11*) $\alpha=0.05$ (two-sided), and $\beta=0.1$, 3350 patients (2 x 1675) will be needed to show a 20% relative risk reduction (RRR) or increase (RRI) corresponding to a 5% absolute risk reduction or risk increase in the primary outcome measure.

Trial Sequential Analysis [63, 64] of existing trials ($n=16$) has showed that 35% (1584 patients) of the required information size to detect or reject a 20% RRR corresponding to 4,575 patients has been accrued [31]. Consequently, there is an information gap of around 3000 patients assuming a 20% RRR in mortality (*appendix 12*). With the inclusion of an additional 3350 patients it is expected that the pooled effect will cross the boundary for benefit/harm or the boundary for futility.

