Appendix 11. Power estimation

All power estimations have been calculated on data from the international SUP-ICU 7-day inception cohort study[57].

Since we do not know whether treatment with acid suppressants reduce or increase mortality, a number of scenarios have been considered (+/- 20 relative risk reduction):

1) 25.0% mortality 90 days after inclusion among patients with:

At least one risk factor*

No acid suppressants at ICU admission

Treatment with acid suppressants during ICU admission

No clinically important bleeding** during ICU admission

Power estimations:

ARR	Power	Patients per group
- 5%	80%	1091
	90%	1461
+ 5%	80%	1248
	90%	1671

We do not know whether PPI benefits or harms the patients, and need to include both scenarios. With 1671 patients in each group we will be able to show an absolute increase in risk of 5% with 90% power at the primary outcome, but also an absolute risk reduction of 5% with 90% power. The sample size has been calculated on patients fulfilling inclusion and exclusion criteria in the SUP-ICU trial and because few patients were not treated with acid suppressants during ICU admission, the estimation is based on the group receiving acid suppressants (intervention group)

2) 25.9% mortality 90 days after inclusion among patients with:

At least one risk factor*

No acid suppressants at ICU admission

Treatment with acid suppressants during ICU admission

Bleeding (overt or clinically important**) or no bleeding during ICU admission

Power estimations:

ARR	Power	Patients per group
- 5,2%	80%	1034
	90%	1384
+5,2%	80%	1180
	90%	1579

3) 29.2% mortality 90 days after inclusion among patients with:

At least one risk factor*

Acid suppressants and no acid suppressants at ICU admission

Treatment with acid suppressants during ICU admission

No bleeding (overt or clinically important**) during ICU admission

Power estimations:

ARR	Power	Patients per group
- 5,8%	80%	901
	90%	1206
+5,8%	80%	1014
	90%	1357

4) 30.5% mortality 90 days after inclusion among patients with:

At least one risk factor*

Acid suppressants or no acid suppressants at ICU admission

Treatment with acid suppressants during ICU admission

Bleeding (overt or clinically important**) or no bleeding during ICU admission

Power estimations:

ARR	Power	Patients per group
- 6,1%	80%	837
	90%	1120
+6,1%	80%	937
	90%	1254

*Risk factors are: shock, renal replacement therapy, coagulopathy and coagulopathy and liver disease as comorbidities)

[figure not shown]

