Because of the widespread use of SUP, no reliable control group for sample size estimation is available and producing reliable sample size estimations according to anticipated effects on GI bleeding is difficult.¹ As a consequence it has been necessary to calculate sample size estimations given that something may change if we withhold PPI until GI bleeding actually happens. Assuming a baseline 90-day mortality of 25%,² $\alpha=0.05$ (two-sided), and $\beta=0.1$, 3350 patients (2 x 1675) will be needed to show a 20% relative risk reduction (RRR) or increase (RRI) corresponding to a 5% absolute risk reduction or increase in the primary outcome measure. Trial Sequential Analysis^{22,23} of existing trials (n=16) has showed that 35% (1584 patients) of the required information size to

detect or reject a 20% RRR or RRI corresponding to 4575 patients has been accrued.⁸

Consequently, there is at least an information gap of around 3000 patients taking a 20% RRR in mortality as a clinically relevant effect size.

Outcome measures

Primary outcome

The primary outcome measure is all-cause mortality within 90 days after randomisation.

Secondary outcomes

1. Proportion of patients with one or more episodes of clinically important GI bleeding, pneumonia, *Clostridium difficile* infection or myocardial ischemia. The events are defined in appendix 1
2. Proportion of patients with one or more episodes of clinically important GI bleeding
3. Proportion of patients with one or more infectious adverse events (pneumonia or *Clostridium difficile* infections)
4. All-cause mortality within 1 year after randomisation
5. Percentage of days alive without use of life support (mechanical ventilation, circulatory support or renal replacement therapy) in the 90-day period
6. The number of patients with one or more serious adverse reactions (SARs) (defined in appendix 2)
7. A health economic analysis will be performed. The analytic details will be based on the result of the trial and specified prior to the analysis.

Pre-planned subgroup analyses

The primary outcome measure will be compared in the following pre-specified subgroups (definitions provided in appendix 2)

1. Shock at randomisation (y/n) (a hypothesised increased intervention effect in patients with shock at randomisation)
2. Mechanical ventilation at randomisation (y/n) (a hypothesised increased intervention effect in patients mechanically ventilated at randomisation)

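### Does the plan lose its 90% power because the 25% mortality comes from patients given acid suppressants?

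*Combined protocol and SAP*

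**What the plan says.** Section 11.1.1 of the protocol states that "3350 patients (2 x 1675) will be needed to show a 20% relative risk reduction (RRR) or increase (RRI") with two-sided alpha 0.05 and beta 0.1. It equates the 20% with 5 percentage points absolute and points to Appendix 11 for the 25%. The abstract (Trial size) gives the same design, "assuming a baseline 90-day mortality of 25"%, and the Sample size section of the SAP opens its calculation with "Assuming a baseline 90-day mortality of 25"%.

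Appendix 11, scenario 1, gives the source of the rate: an inception cohort, restricted to patients who received acid suppressants in the ICU. Few patients went untreated, so "the estimation is based on the group receiving acid suppressants (intervention group"). On direction it says "We do not know whether PPI benefits or harms the patients, and need to include both scenarios", and on size "With 1671 patients in each group we will be able to show an absolute increase in risk of 5% with 90% power".

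Section 1.6.2 says there is no reliable control group and that the calculation was made "given that something may change if we stop/avoid PPI until GI bleeding actually happens". The SAP says much the same: "given that something may change if we withhold PPI until GI bleeding actually happens".

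**The concern.** One figure appears to have two roles. A baseline rate is usually read as the rate without the experimental treatment, and section 11.1.2 uses the word that way for GI bleeding (3% falling to 2%). Appendix 11 attaches the 25% to treated patients and calls them the intervention group. No passage names the arm that has the 25%.

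For a relative effect this could matter. If pantoprazole mortality is 25% and placebo is the reference, a 20% increase is a gap of 4.17 points, not 5, and the chance of missing it is about 18% instead of the stated 10%. Harm is also a direction the investigators care about: section 1.6.1 raises possible hidden excess mortality under prophylaxis, and section 1.6.2 discusses a 10-20% relative increase.

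**Working it through.** **Inputs.** Mortality 25% (section 11.1.1; Appendix 11, scenario 1); difference 5 points; two-sided alpha 0.05; power 90%; 1:1 allocation; 1675 per arm.

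**1. Reproduce the plan's sample sizes.** Normal approximation, unpooled variance:

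n per arm = (z₀.₉₇₅ + z_power)² × [p₁(1−p₁) + p₂(1−p₂)] / (p₁−p₂)²

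For 90% power, (1.960 + 1.2816)² = 10.507.

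- 25% against 30%: 10.507 × (0.1875 + 0.2100) / 0.0025 = 1670.7, so 1671.
- 25% against 20%: 10.507 × (0.1875 + 0.1600) / 0.0025 = 1460.5, so 1461.

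Both match Appendix 11, as do its 80% rows (1248 and 1091). With pooled variance the 90% figures are 1674 and 1464. The 1675 is sound.

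**2. Power at 1675 per arm for the stated 5 points.** Power = Φ(|p₁−p₂| / SE − 1.960), with SE = √{[p₁(1−p₁) + p₂(1−p₂)] / 1675}.

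- 25% against 30%: SE = 0.01540; 0.05 / 0.01540 − 1.960 = 1.286; power 90.1%.
- 25% against 20%: SE = 0.01440; 0.05 / 0.01440 − 1.960 = 1.511; power 93.5%.

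The formula is symmetric in the two arms, so the results do not depend on which arm has the 25%.

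**3. Which rate is the denominator of the 20%?** Compare each Appendix 11 rate with the difference printed beside it:

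| Rate | 20% of the rate | Difference in Appendix 11 |
|---|---|---|
| 25.0% | 5.00 | 5 |
| 25.9% | 5.18 | 5.2 |
| 29.2% | 5.84 | 5.8 |
| 30.5% | 6.10 | 6.1 |

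In every scenario, and in both directions, the difference is 20% of the quoted rate. All eight 90%-power sample sizes follow from those differences by the formula in step 1 (1461/1671, 1384/1579, 1206/1357, 1120/1254). The reference is therefore the group with the quoted rate, although no arm is named.

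**4. The three possible readings at 1675 per arm.**

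| Reading | 20% increase | 20% reduction |
|---|---|---|
| 25% assumed for placebo, placebo the reference | 25% vs 30%: 90% | 25% vs 20%: 93% |
| 25% under PPI care, which is the reference; the 20% is the change on withholding PPI | 25% vs 30%: 90% | 25% vs 20%: 93% |
| 25% in the PPI arm, but placebo the reference | 20.83% vs 25%: 82% | 31.25% vs 25%: 98% |

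In the third row, placebo is 25% / 1.2 = 20.83% or 25% / 0.8 = 31.25%. For the increase, SE = 0.01451 and 0.04167 / 0.01451 − 1.960 = 0.912, giving 81.9%; 90% power would need about 2133 per arm. For the reduction, SE = 0.01550 and 0.0625 / 0.01550 − 1.960 = 2.073, giving 98.1%.

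The third row breaks the plan's own equation: the differences become 4.17 and 6.25 points. With placebo as reference, a 5-point gap around a pantoprazole rate of 25% would be a 25% increase (20% to 25%) or a 16.7% reduction (30% to 25%). The first two rows keep the equation.

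**The case for a change.** The strongest case for the concern is that a reader has to choose a reading before the headline power can be confirmed. Section 11.1.2 supports baseline as the untreated rate, Appendix 11 says intervention group, and Appendix 11 asks whether PPI helps or harms, which makes no PPI the natural comparator. Put together, these give the 82%. A placebo rate near 21% also has some support: Appendix 12 uses 21% for control arms of earlier trials, and 21% against 25.2% likewise gives about 82% at 1675 per arm.

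Part of this stands. The labels do not agree, and the 82% is correctly computed. What does not stand is that it contradicts the stated power. It joins Appendix 11's label to a placebo denominator that the appendix's own differences rule out. It is also one side of a trade: on the same reading, power for a 20% reduction rises to 98%. At the other Appendix 11 rates (25.9%, 29.2%, 30.5%), power for a 20% increase on that reading is 84%, 89% and 91%.

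The 21% raises a different matter, namely that a lower reference rate reduces power for a fixed relative effect. That is true of any such calculation. Moreover, section 1.6.1 doubts that the earlier trials recorded mortality reliably beyond the ICU or hospital stay, so the 21% is not clearly a 90-day rate.

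**Conclusion.** No change follows. The sample size is right, and power is at least 90% (90% and 93%) for the difference the plan defines: 5 points, or 20% of a 25% reference rate, whichever arm has that rate. The 82% applies only if 25% is the pantoprazole rate and the relative increase is taken against placebo, a combination the plan does not state and its figures do not fit.

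Using a treated cohort as a stand-in is a fair approximation when almost no one goes untreated. Appendix 11 says that this was done and why, section 11.1.1 refers the reader there, and section 1.6.2 and the SAP admit that no reliable control group exists. What is left is an unnamed arm. Naming it would not alter the 3350 patients, the logistic regression of 90-day mortality, the interim analysis (set by patient counts) or the trial's conclusion, none of which uses the 25% once the size is fixed.

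These results rest on the normal approximation without allowance for dropout, which the plan also does not make. With a continuity correction, 25% against 30% gives 89% and 20.83% against 25% gives 81%, so the comparison is the same.

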Appendix 12. Trial sequential analysis of all-cause mortality (16 trials).

A diversity adjusted information size of 4,675 patients was calculated using $\alpha=0.05$ (two sided), $\beta=0.10$ (power 90%), an anticipated diversity at the time when conclusive evidence has been reached ($D^2=20\%$), an anticipated relative risk reduction of 20%, and an event proportion of 21% in the placebo/control arm. The blue cumulative z curve was constructed using a random effects model. The pooled effect is a RR=0.98 with a TSA adjusted 95% confidence interval of (0.75 to 1.28)

Appendix 13. International Committee of Medical Journal Editors (ICMJE) form for potential conflicts of interest.

ICMJE Form for Disclosure of Potential Conflicts of Interest

Instructions

The purpose of this form is to provide readers of your manuscript with information about your other interests that could influence how they receive and understand your work. The form is designed to be completed electronically and stored electronically. It contains programming that allows appropriate data display. Each author should submit a separate form and is responsible for the accuracy and completeness of the submitted information. The form is in six parts.

1. Identifying information.

2. The work under consideration for publication.

This section asks for information about the work that you have submitted for publication. The time frame for this reporting is that of the work itself, from the initial conception and planning to the present. The requested information is about resources that you received, either directly or indirectly (via your institution), to enable you to complete the work. Checking "No" means that you did the work without receiving any financial support from any third party – that is, the work was supported by funds from the same institution that pays your salary and that institution did not receive third-party funds with which to pay you. If you or your institution received funds from a third party to support the work, such as a government granting agency, charitable foundation or commercial sponsor, check "Yes".

3. Relevant financial activities outside the submitted work.

This section asks about your financial relationships with entities in the bio-medical arena that could be perceived to influence, or that give the appearance of potentially influencing, what you wrote in the submitted work. You should disclose interactions with ANY entity that could be considered broadly relevant to the work. For example, if your article is about testing an epidermal growth factor receptor (EGFR) antagonist in lung cancer, you should report all associations with entities pursuing diagnostic or therapeutic strategies in cancer in general, not just in the area of EGFR or lung cancer.

Report all sources of revenue paid (or promised to be paid) directly to you or your institution on your behalf over the 36 months prior to submission of the work. This should include all monies from sources with relevance to the submitted work, not just monies from the entity that sponsored the research. Please note that your interactions with the work's sponsor that are outside the submitted work should also be listed here. If there is any question, it is usually better to disclose a relationship than not to do so.

For grants you have received for work outside the submitted work, you should disclose support ONLY from entities that could be perceived to be affected financially by the published work, such as drug companies, or foundations supported by entities that could be perceived to have a financial stake in the outcome. Public funding sources, such as government agencies, charitable foundations or academic institutions, need not be disclosed. For example, if a government agency sponsored a study in which you have been involved and drugs were provided by a pharmaceutical company, you need only list the pharmaceutical company.

4. Intellectual Property.

This section asks about patents and copyrights, whether pending, issued, licensed and/or receiving royalties.

5. Relationships not covered above.

Use this section to report other relationships or activities that readers could perceive to have influenced, or that give the appearance of potentially influencing, what you wrote in the submitted work.

Definitions.

Entity: government agency, foundation, commercial sponsor, academic institution, etc.

Grant: A grant from an entity, generally [but not always] paid to your organization

Personal Fees: Monies paid to you for services rendered, generally honoraria, royalties, or fees for consulting, lectures, speakers bureaus, expert testimony, employment, or other affiliations

Non-Financial Support: Examples include drugs/equipment supplied by the entity, travel paid by the entity, writing assistance, administrative support, etc.

Other: Anything not covered under the previous three boxes

Pending: The patent has been filed but not issued

Issued: The patent has been issued by the agency

Licensed: The patent has been licensed to an entity, whether earning royalties or not

Royalties: Funds are coming in to you or your institution due to your patent

ICMJE Form for Disclosure of Potential Conflicts of Interest

Section 1. Identifying Information

1. Given Name (First Name)

2. Surname (Last Name)

3. Date

4. Are you the corresponding author?

 Yes No

5. Manuscript Title

6. Manuscript Identifying Number (if you know it)

Section 2. The Work Under Consideration for Publication

Did you or your institution **at any time** receive payment or services from a third party (government, commercial, private foundation, etc.) for any aspect of the submitted work (including but not limited to grants, data monitoring board, study design, manuscript preparation, statistical analysis, etc.)?

Are there any relevant conflicts of interest? Yes No

ADD

Section 3. Relevant financial activities outside the submitted work.

Place a check in the appropriate boxes in the table to indicate whether you have financial relationships (regardless of amount of compensation) with entities as described in the instructions. Use one line for each entity; add as many lines as you need by clicking the "Add +" box. You should report relationships that were **present during the 36 months prior to publication**.

Are there any relevant conflicts of interest? Yes No

ADD

Section 4. Intellectual Property -- Patents & Copyrights

Do you have any patents, whether planned, pending or issued, broadly relevant to the work? Yes No

ICMJE Form for Disclosure of Potential Conflicts of Interest

Section 5. Relationships not covered above

Are there other relationships or activities that readers could perceive to have influenced, or that give the appearance of potentially influencing, what you wrote in the submitted work?

- Yes, the following relationships/conditions/circumstances are present (explain below):
- No other relationships/conditions/circumstances that present a potential conflict of interest

At the time of manuscript acceptance, journals will ask authors to confirm and, if necessary, update their disclosure statements. On occasion, journals may ask authors to disclose further information about reported relationships.

Section 6. Disclosure Statement

Based on the above disclosures, this form will automatically generate a disclosure statement, which will appear in the box below.

Generate Disclosure Statement

Evaluation and Feedback

Please visit <http://www.icmje.org/cqi-blm/feedback> to provide feedback on your experience with completing this form.

Summary of changes to the original protocol

Amendments to the previously approved protocol entitled 'Stress ulcer prophylaxis with proton pump inhibitor (pantoprazole) in adult critically ill patients in the intensive care unit: A randomised, blinded, placebo-controlled trial', version 3.0, October 20th, 2015.

Amendment 1 (August 2016)

